#### 6.5.2. Adverse Event and Concomitant Medication End Dates

If the start date is non-missing and the imputed end date is before the start date, the start date will be used as the end date. If the death date is available and the imputed end date is after the death date, the death date will be used as the end date. If an imputation for an AE end date results in an AE end date that is after the EODB period date/EOS date, the AE will be considered as ongoing at the EODB period date/EOS date.

- (1) Missing day only
  - The last day of the month will be used.
- (2) Missing day and month
  - 31 December will be used.
- (3) Missing day, month, and year
  - The event will be regarded as ongoing.

#### 6.5.3. Exposure

No imputation will be done for the date of the first dose of study drug.

If the date of the last dose of study drug is missing or partially missing, it will be imputed as follows (separately for each period):

- If the last date of study drug is completely missing and there is no End of Treatment Disposition electronic case report form (eCRF) page for the study drug AND there is no death date, the subject should be considered to be ongoing and the EODB period date/EOS date, will be used as the last dosing date.
- If the last date of study drug is completely or partially missing and there is EITHER an End of Treatment Disposition eCRF page for the study drug OR a death date (on or before the EODB period date/EOS date), then the imputed last dose date is:

=Last day of the year, if only the year is available and Year <Year of min(EOT date, death date)

=Last day of the month, if both the year and month are available and Year=Year of min(EOT date, death date) and Month <Month of min(EOT date, death date)

=min(EOT date, death date), for all other cases

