#### 6.3.2. Start and End Dates of Study Treatment

The start of study treatment is the earliest date/time of administration of a non-zero dose of the study drug.

The end of study treatment is the latest date/time of administration of a non-zero dose of the study drug on or before the EODB period date/ EOS date.

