#### 6.3.5. On-Treatment Period

The on-treatment period starts on the date of the start of study treatment and ends 28 days after the end of study treatment (including dose taper period).

Within the on-treatment period, there are two distinct treatment periods:

- Double-blind on-treatment period starts on the date of the start of study treatment and ends
  - 28 days after the end of study treatment, for subjects who discontinue study treatment during the Double-blind Period of the study
  - Before the start of the OLE treatment period, for subjects who continue onto the OLE Period of the study

• OLE on-treatment period applies only to subjects who complete the Double-blind Period of the study, and starts with the first dose of open-label mitapivat in the OLE Period and ends 28 days after the end of study treatment

For subjects who receive mitapivat in the OLE Period, assessments or events occurring on the date of first dose of mitapivat in the OLE Period will be included in the analysis of the data from the double-blind on-treatment period, except for AEs and concomitant medications reported for subjects in the placebo arm which will be included only in the analysis of the data from the OLE on-treatment period.

Data listings will include all assessments and events, with those that occur outside of the on-treatment period flagged.

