#### 7.4.1. Treatment Duration and Exposure

Duration of exposure to study drug will be summarized as a continuous variable as well as in categories.

• Duration of exposure (days) = (last dose date-first dose date + 1)

Duration of exposure (weeks) = (last dose date-first dose date + 1) / 7

Duration of exposure (years) = (last dose date-first dose date + 1) / 365.25

• Double-blind Period: the categories will be >0-6, >6-12, >12-24, and >24 weeks

• OLE Period: the categories will be >0-0.5, >0.5-1, >1-2, >2-3, >3-4, >4-≤5, and >5 years.

Compliance will be summarized based on percentage of tablets taken, where

- Percentage of tablets taken =100×(total number of tablets administered)/(total number of tablets intended)
- Total number of tablets administered = total number of tablets dispensed tablets returned
- Duration of prescription = end date of prescription start date of prescription +1
- Total number of tablets intended = sum of number of tablets intended over all prescription periods
- Number of tablets intended during each prescription period = prescribed dosing frequency × number of tablets intended for each administration × duration of the prescription. Prescribed dosing frequency takes value of 1 and 2 for QD and BID, respectively

Percentage of tablets taken will be summarized by treatment arm. The frequency of subjects whose compliance is <80%, 80-100%, >100-120%, and >120% will be summarized.

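### SAP 6.5.3 moves a last dose with known month and year to the end-of-treatment or death date when that date falls in a later calendar year, which overstates exposure

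*SAP*

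**What the plan says.** SAP Section 6.5.3 (Exposure) imputes the last dose date separately for each period. The relevant rules start: "If the last date of study drug is completely or partially missing and there is EITHER an End of Treatment Disposition eCRF page", or a death date on or before the reporting cut-off. Write M for the earlier of the EOT date and the death date. Three rules follow.

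1. Year known, month unknown: "Last day of the year, if only the year is available and Year <Year of min(EOT date, death date").
2. Year and month known: "Last day of the month, if both the year and month are available and Year=Year of min(EOT date, death date"), with the further condition "and Month <Month of min(EOT date, death date").
3. Everything else: "min(EOT date, death date), for all other cases".

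The imputed date is used in two places. Section 7.4.1 defines "Duration of exposure (days) = (last dose date-first dose date + 1"). Section 6.3.2 states: "The end of study treatment is the latest date/time of administration of a non-zero dose of the study drug". Section 6.3.5 then builds on that end date: "The on-treatment period starts on the date of the start of study treatment and ends 28 days after the end of study treatment". Entry to the Open-label Extension (OLE) is handled differently: Section 6.3.5 closes the double-blind window of those subjects just before OLE treatment starts, so that window does not use the imputed date.

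**The concern.** Rules 1 and 2 exist to stop the imputed date from running past the period that the site recorded. One class of record escapes both: day missing, month and year known, and M in a later calendar year. Rule 1 does not apply because the month is known. Rule 2 does not apply because the years differ. Rule 3 then assigns M, which is later than any day in the recorded month. A fuller record therefore gets a worse date than a year-only record.

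The error always lengthens exposure. Where the on-treatment window runs from the last dose, it also lengthens that window, which decides whether an adverse event is treatment-emergent (7.7.1), which laboratory grades count (7.7.3) and whether a death is on-treatment or post-treatment (7.7.2).

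**Working it through.** The documents state no figure for this rule, so there is none to reproduce. The check applies the three rules literally and compares them with a version in which rule 2 applies whenever the recorded year-month precedes the year-month of M.

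**Inputs.** The rules are from SAP 6.5.3, exposure = last dose − first dose + 1 is from 7.4.1, and window end = last dose + 28 days is from 6.3.5. All calendar dates below are assumed for illustration, with first dose on 1 Sep 2022.

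| Recorded last dose | M | SAP result | Corrected result | Excess (days) | Exposure in days, SAP / corrected |
|---|---|---|---|---|---|
| Oct 2022 | 20 Nov 2022 | 31 Oct 2022 | 31 Oct 2022 | 0 | 61 / 61 |
| 2022 only | 20 Jan 2023 | 31 Dec 2022 | 31 Dec 2022 | 0 | 122 / 122 |
| Dec 2022 | 1 Jan 2023 | 1 Jan 2023 | 31 Dec 2022 | 1 | 123 / 122 |
| Dec 2022 | 20 Jan 2023 | 20 Jan 2023 | 31 Dec 2022 | 20 | 142 / 122 |
| Nov 2022 | 20 Jan 2023 | 20 Jan 2023 | 30 Nov 2022 | 51 | 142 / 91 |
| Oct 2022 | 10 Feb 2023 | 10 Feb 2023 | 31 Oct 2022 | 102 | 163 / 61 |

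**The Nov 2022 row.** From 30 Nov to 20 Jan is 31 + 20 = 51 days. Exposure from 1 Sep to 30 Nov is 30 + 31 + 30 = 91 days; the SAP rule gives 91 + 51 = 142. The window should end no later than 30 Nov + 28 days = 28 Dec 2022; the SAP rule ends it on 20 Jan + 28 days = 17 Feb 2023.

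**Exposure category.** In the last row, 61/7 = 8.7 weeks and 163/7 = 23.3 weeks, so the subject moves from the >6-12 to the >12-24 week band of 7.4.1.

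**Internal inconsistency.** With M = 20 Jan 2023, a record of 2022 alone gives 31 Dec 2022, but the more complete Nov 2022 gives 20 Jan 2023.

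**Scope.** Take every M from 1 Jan 2021 to 31 Dec 2023 with every recorded month from Jan 2021 up to M: 20,286 combinations. Of these, 365 × 12 + 365 × 24 = 13,140 cross a calendar year. In all 13,140 the SAP rule gives a date after the recorded month ended. In the other 20,286 − 13,140 = 7,146 same-year combinations the two versions agree.

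**Elsewhere in the SAP.** Section 6.5.1 compares month and year jointly with the reference date, and Section 6.5.2 uses the month end whenever only the day is missing. Neither corrects 6.5.3, and nothing else in the SAP or protocol does.

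**The case against.** The strongest reply accepts the logic gap and disputes its consequences. Most of that reply stands.

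- **Little data fall in the extra window.** Protocol 9.2.1 and 9.3.1 end routine adverse event recording 28 days after the last dose; after that only related serious events are reported. The Safety Follow-up visit is at 28 days ± 4 (Protocol Table 2), with nothing scheduled later. For subjects who stop in the Double-blind Period, data after the end of safety follow-up are not used in the primary report (SAP 2 and 6.4.1). A reader might infer that the longer window fills with adverse events and laboratory grades. The documents do not support that: what remains is the visit tolerance, unscheduled data and late related serious events.
- **The primary endpoint.** A reader might also infer a threat through the requirement for two on-treatment hemoglobin values (SAP 7.6.1). For subjects entering the OLE the double-blind window does not use the imputed date, and those who stop early have no scheduled hemoglobin after Safety Follow-up. Any effect is marginal.
- **The size of the gap is assumed.** The SAP does not define the EOT date. If it sits close to the last dose, the excess is a matter of days. Gaps of many months are hard to reconcile with OLE visits at most 12 weeks apart and drug dispensed and returned at each.
- **No planned comparison is shown to move.** Exposure is descriptive, the bands are wide, adverse events are summarized as subject frequencies, and the rule is the same in both arms.

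Three things survive. Rules 1 and 2 themselves presuppose that M can fall in a later month or year than the last dose. Exposure is also summarized as a continuous variable, so it shifts even when no band is crossed. And a death can be misclassified: with last dose in Nov 2022, death on 20 Jan 2023 and no earlier EOT date, the window should close by 28 Dec 2022, yet the rule sets the last dose to the day of death and makes the death on-treatment. For a subject who stopped in the Double-blind Period this needs follow-up to be still open, since the latest on-time visit would be 30 Nov + 32 days = 1 Jan 2023. It is more plausible at the end of OLE treatment.

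**Conclusion.** The rule is wrong as written. Every last-dose record with the day missing, the month and year known, and M in a later calendar year receives a date that the record itself excludes, and duration of exposure is overstated. The on-treatment window is also extended for subjects who discontinue in the Double-blind Period and at the end of OLE treatment. The double-blind window of subjects who enter the OLE is unaffected, although their double-blind exposure can still be overstated.

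The logic follows from the text alone. The size does not: the 51-day example rests on assumed dates, and the documents give neither the number of affected records, probably small, nor a definition of the EOT date. The practical consequence is a modest error in exposure summaries and an occasional late event, such as a death, counted as on-treatment. No material effect on the primary endpoint is shown, and sample size and power do not depend on the rule. It should be corrected before unblinding as a drafting error.

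**What to change.** Replace the second rule in SAP 6.5.3 with: *Last day of the recorded month, if year and month are available and the recorded year-month is earlier than the year-month of min(EOT date, death date).* Leave the first and third rules unchanged.

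The cost is one line of SAP text and the matching line of code. Same-year results do not change, and the comparison then matches the joint month-and-year comparison already used in SAP 6.5.1. There is no statistical downside.

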#### 6.5.4. Death Date

Missing or partial death dates will not be imputed.

#### 6.5.5. Pharmacokinetic Data

#### 6.5.5.1. Handling of Missing Concentrations

Missing concentrations before the first dose of study treatment will be set to 0 in the analysis. A concentration is deemed missing if the PK sample is not collected, or the PK sample is collected but the concentration is not reportable.

In addition:

- If ≤2 samples have concentrations ≥LLQ, none of the PK parameters will be derived.
- If pre-dose concentrations are missing at a steady-state visit, PK parameters associated with that visit will not be derived with the exception of  $C_{max}$  and  $T_{max}$ .

Since the protocol allows a  $\pm 30$  minutes window for the 7-hour PK sample collection, if the end time of the predefined area under the concentration-time curve falls outside the range of the available data then:

- the AUC0-last will be used to represent AUC0-7, if  $T_{last} \ge 6.5$  h.
- AUC0-7 will not be reported, if  $T_{last} < 6.5$  h.

## 6.5.5.2. Incomplete Dosing Information

Samples associated with incomplete dosing information (ie, missing dosing date, dosing time, actual dose received, and/or dosing schedule) will be excluded from the analysis. The missing dosing information will not be imputed.

#### 6.5.5.3. Missing Sampling Dates or Times

Samples associated with missing sample dates and/or times will be excluded from the analysis. The missing sampling dates and/or times will not be imputed.

## 6.5.5.4. Incomplete Concentration-time Data

Subjects who have incomplete concentration-time profiles (ie, missing concentrations at more than one scheduled time point) may be excluded from the PK analysis set. The decision will be made by the unblinded clinical pharmacologist before the study is unblinded for the analysis of the primary endpoint.

# 7. STATISTICAL ANALYSES

## 7.1. Subject Disposition

For all subjects screened in the study, the following will be summarized:

- Number of subjects screened in the study
- Frequency (number and percentage) of subjects who discontinued the study before randomization, overall and by reason for discontinuation. Percentages will be calculated based on the number of subjects screened in the study.

In addition, the frequency of subjects in each of the analysis sets described in Section 5 will be summarized by treatment arm. Percentages will be calculated only for analysis sets that are a subset of the FAS or a subset of the safety analysis set.

The following summaries will be presented by treatment arm based on the FAS or (for the summaries associated with the OLE Period only) the OLE analysis set:

- Frequency of subjects in each randomization strata and combination of randomization strata (per IXRS)
- Frequency of subjects randomized in each geographic region, country, and site
- Frequency of subjects randomized and not treated, overall and by reason for discontinuation
- Frequency of subjects who completed the Double-blind Period
- Frequency of subjects with study drug ongoing in the Double-blind Period
- Frequency of subjects who discontinued study drug in the Double-blind Period, overall and by the reason for discontinuation of study drug
- Frequency of subjects who completed the OLE Period
- Frequency of subjects with study drug ongoing during the OLE Period
- Frequency of subjects who discontinued study drug in the OLE Period, overall and by the reason for discontinuation of study drug
- Frequency of subjects who completed the safety follow-up period
- Frequency of subjects ongoing in the safety follow-up period
- Frequency of subjects who discontinued the safety follow-up period, overall and by the reason for discontinuation
- Frequency of subjects who completed the study
- Frequency of subjects ongoing in the study
- Frequency of subjects who discontinued the study, overall and by reason for discontinuation; the reason for discontinuation will be derived as the reason associated with the earliest epoch that was discontinued.

The frequency of subjects with disposition reason, in each epoch, due to reasons associated with COVID-19 will further be summarized under the main reason for discontinuation.

In addition, cross-tabulation of subjects randomized (mitapivat, matched placebo) vs subjects who have received at least 1 dose of study drug (mitapivat, matched placebo) in the Double-blind Period will be performed.

Disposition for all screened subjects and randomization data will be provided in by-subject listings.

## 7.2. **Protocol Deviations**

All major protocol deviations that impact the safety of the subjects, the conduct of the study, or the evaluation of the study results will be reported by treatment arm based on the FAS or (for the summaries associated with the OLE Period only) the OLE analysis set. These will include:

- Subjects randomized despite not satisfying the eligibility criteria
- Subjects who develop withdrawal criteria while on the study but are not withdrawn
- Subjects who receive a study drug different from that assigned at randomization
- Subjects who are randomized under the wrong stratification factor(s)
- Subjects who receive an excluded concomitant medication

In addition, for each category of major protocol deviations, those related to COVID-19 will be summarized.

Major protocol deviations will be provided in a by-subject listing.

## 7.3. Demographic and Other Baseline Characteristics

The following summaries will be presented by treatment arm and overall based on the FAS or (for the summaries associated with the OLE Period only) the OLE analysis set, unless otherwise specified.

## 7.3.1. Demographics and Physical Measurements

Demographic characteristics and physical measurements at baseline will be summarized as follows:

- Demographic characteristics
  - Sex: male, female (child-bearing potential status will be summarized for female subjects), unknown
  - Race: American Indian or Alaska Native, Asian, Black or African American, Native Hawaiian or other Pacific Islander, White, multiracial, unknown, not reported
  - Ethnic origin: Hispanic or Latino, not Hispanic or Latino, not reported

- Age (years): summary statistics
- Age categories:
  - <65 years,  $\geq 65$  years
  - <35 years,  $\geq 35$  years
- Physical measurements
  - Height (cm)
  - Weight (kg)
  - BMI  $(kg/m^2)$

Demographic data for all screened subjects will be provided in a by-subject listing.

#### 7.3.2. Disease Characteristics

In addition to randomization stratification factors (Section 7.1) and baseline for diseaserelated clinical laboratory assessments, the following baseline characteristics of the underlying disease will be summarized based on the data entered in the eCRF:

- Transfusion burden (number of RBC units transfused in the 24-week period before randomization) in categories: 0, 1-2, 3-5, >5.
- Splenectomy status (Yes, No; if Yes, age of splenectomy)
- Prior cholecystectomy status (Yes, No; if Yes, age of cholecystectomy)
- Prior Iron chelation status (Yes, No); the status is "Yes" if a subject has received chelation therapy within 1 year (365 days) before randomization
- Prior hydroxyurea status (Yes, No)
- DXA scan results by location (hip and spine): BMD and their corresponding T-scores and Z-scores. Frequency of subjects with worst T-score in 3 categories (≤-2.5, >-2.5-<-1, ≥-1.0) by location and across the two locations.

Data on disease characteristics will be provided in by-subject listings.

## 7.3.3. Medical and Surgical History

Medical and surgical history will be summarized in frequency tabulations according to the latest version of the Medical Dictionary for Regulatory Activities (MedDRA) by System Organ Class (SOC) and Preferred Term (PT).

Medical and surgical history will be provided in by-subject listings.

#### 7.3.4. **Prior Therapies**

The following summaries will be presented by treatment arm and overall based on the safety analysis set.

**Prior medications** are defined as medications (from the "Prior and Concomitant Medications" eCRF) that are started before the start of study treatment.

All non-study medications will be coded according to the Anatomical Therapeutic Chemical (ATC) code and PT using the latest version of the World Health Organization (WHO) Drug Dictionary. All prior medications will be summarized in frequency tabulations according to the WHO ATC third level and PT.

**Prior procedures** are defined as procedures (from the "Prior and Concomitant Procedures" eCRF) that are started before the start of study treatment.

The prior procedures will be coded according to the latest version of the MedDRA by SOC and PT and will be summarized in frequency tabulations by SOC and PT.

Prior medications and prior procedures will be provided in by-subject listings.

## 7.4. Exposure to Study Drug and Compliance

The following summaries will be presented by treatment arm based on the safety analysis set for the Double-blind Period using "Prescribed Dose", "First Dose of Study Medication (Double-blind Period)", and "Study Drug Dispensation and Return" eCRFs; and the OLE analysis set for the OLE Period using the "Prescribed Dose", "First Dose of Study Medication (Open-label Extension Period)", and "Study Drug Dispensation and Return" eCRFs.

Subjects will receive 100 mg BID mitapivat or matched placebo for oral administration. Subjects who discontinue study drug should undergo the recommended dose taper. Study drug dose and recommended dose taper are provided in Table 4.

Level	Dose	Schedule
Full dose	100 mg	BID
Taper dose	100 mg	QD for 7 days, then discontinue study drug

 Table 4:
 Study Drug Dose and Recommended Dose Taper Regimen

Abbreviations: BID = twice daily; QD = once daily

#### 7.4.1. Treatment Duration and Exposure

Duration of exposure to study drug will be summarized as a continuous variable as well as in categories.

• Duration of exposure (days) = (last dose date-first dose date + 1)

Duration of exposure (weeks) = (last dose date-first dose date + 1) / 7

Duration of exposure (years) = (last dose date-first dose date + 1) / 365.25

• Double-blind Period: the categories will be >0-6, >6-12, >12-24, and >24 weeks

• OLE Period: the categories will be >0-0.5, >0.5-1, >1-2, >2-3, >3-4, >4-≤5, and >5 years.

Compliance will be summarized based on percentage of tablets taken, where

- Percentage of tablets taken =100×(total number of tablets administered)/(total number of tablets intended)
- Total number of tablets administered = total number of tablets dispensed tablets returned
- Duration of prescription = end date of prescription start date of prescription +1
- Total number of tablets intended = sum of number of tablets intended over all prescription periods
- Number of tablets intended during each prescription period = prescribed dosing frequency × number of tablets intended for each administration × duration of the prescription. Prescribed dosing frequency takes value of 1 and 2 for QD and BID, respectively

Percentage of tablets taken will be summarized by treatment arm. The frequency of subjects whose compliance is <80%, 80-100%, >100-120%, and >120% will be summarized.

